## STUDY SUMMARY

Study Title	Exploring perspectives on Palliative and Supportive Care, to inform recommendations to help people live well with inflammatory arthritis throughout the disease course.
Internal ref. no. (or short title)	ENRICH
Study Design	Qualitative and quantitative
Study Participants	
 
• People living with inflammatory arthritis
 
• Healthcare practitioners working in Rheumatology, Palliative and End of Life Care (PEoLC), Primary Care and Community (GPs, district nurses, community therapists)
 
• Representatives from relevant charities and organisations
 
• Commissioners of health and social care services
 

Planned Size of Sample (if applicable)	Work-package 1: 15-30 participant interviews Work-package 2: minimum of 50 survey responses from healthcare practitioners.
Follow up duration (if applicable)	N/A
Planned Study Period	20 months

## FUNDING AND SUPPORT IN KIND

FUNDER(S) (Names and contact details of ALL organisations providing funding and/or support in kind for this study)	FINANCIAL AND NON FINANCIAL SUPPORT GIVEN
Arthritis UK	Financial support for the costs of conducting this project.

## ROLE OF STUDY SPONSOR AND FUNDER

The sponsor, Dorothy House Hospice, has overall responsibility for the initiation and management of the study. This includes the development of the study design, conduct, data analysis and interpretation, any manuscript(s) and other dissemination arising, and any decisions regarding any of these aspects of the study.

The Funder's terms and conditions-please see Arthritis UK Contracts and Terms and Conditions

## **ROLES AND RESPONSIBILITIES OF STUDY MANAGEMENT COMMITTEES/GROUPS & INDIVIDUALS**

Prior to commencement of recruitment to the study, and beyond any required HRA/NHS ethical approvals, governance approvals will be required from the Bath Swindon and Wiltshire (BSW) Research Hub, Dorothy House Research Committee, Dorothy House Clinical Governance Committee and Dorothy House Chief Executive Officer.

Whilst some members of the study team sit on the Dorothy House Research Committee and the BSW Research Hub Executive, governance approvals will remain independent of the team members involved in the study.

The study team comprises patient and public representation and representatives from across the five collaborating organisations (Dorothy House Hospice; Royal United Hospitals NHS Foundation Trust; University of the West of England; University Hospitals Bristol and Weston NHS Foundation Trust; Elm Tree Surgery, Shrivenham).

Dorothy House regularly engages with Patient and Public Contributors via the Hospice User Group (HUG). The Research Committee also includes a lay member. We will include two patient and public contributors in the study team to provide ongoing input to the conduct of the study and to analysis, reporting and dissemination activities.

A Steering Committee will be formed and include patient and public representation, a methodologist relevant to the project design, and healthcare representation from Palliative and End of Life care, Rheumatology and Primary care.

## **STUDY TIMELINE**

The study described below will run from January 2026-April 2027. Please see Gantt chart for details (Appendix 1)

## STUDY PROTOCOL

Exploring perspectives on Palliative and Supportive Care, to inform recommendations to help people live well with inflammatory arthritis throughout the disease course.

### 1 BACKGROUND & RATIONALE

Palliative Care helps people with life-limiting illnesses live as well as possible. It focuses on improving quality of life, not just for patients, but also for their families. This care looks at the whole person, including physical comfort, emotional wellbeing, and spiritual needs. Palliative care is about helping people live fully, even as they approach the end of life. It is delivered by a multi-disciplinary team of healthcare professionals across many settings like hospitals, care homes, hospices, and a person's home.

The recently updated NHS England Ambitions for Palliative and End of Life Care Framework specifies high quality palliative and end of life care should be available to anyone with a life limiting illnesses, regardless of their diagnosis. Despite this, it is most commonly offered to people with cancer, heart disease, lung conditions, and AIDS. Inequalities of access are known to exist particularly for people with non-malignant conditions. This is especially true for those with multiple long-term illnesses, including those with an Inflammatory Arthritis such as: rheumatoid arthritis (RA), psoriatic arthritis (PsA), juvenile idiopathic arthritis (JIA), or axial spondyloarthritis (axSpA). The high incidence of rheumatic and musculoskeletal diseases, and associated chronic pain, mean these conditions often comprise one or more of the multimorbidity conditions an individual may be living with.

Palliative care can begin as soon as someone is diagnosed with a life-limiting illness, and some hospices provide care from the last 1,000 days of life, but in cancer care, for example, a broader approach called Palliative and Supportive Care (PSC) is now used, with 'Supportive Care' being provided much earlier in a person's disease course.

#### **Palliative and Supportive Care**

PSC aims to support people and those close to them throughout the illness, meeting a wide range of needs: physical, emotional, social, spiritual, and cultural. Recent research has recommended a more inclusive definition of PSC, which would apply to anyone with a serious or chronic illness, and not just people with a cancer diagnosis. For example, PSC is now widely adopted in non-cancer conditions, such as cardiac, renal, and neurological diseases. Starting PSC early has been shown to improve quality of life, extend survival, and reduce the need for aggressive treatments at the end of life. This approach could also help people with inflammatory arthritis live better, more comfortable lives.

#### **Inflammatory Arthritis**

These conditions can cause long-term pain, stiffness, fatigue, and disability. They may also affect other parts of the body, like the lungs, skin, eyes, and bowel. These secondary complications, and the side effects of medications used to help

slow the progression of the disease or improve symptoms, can shorten life expectancy, for example, people with Rheumatoid Arthritis and associated lung disease may live only 3–7 years after diagnosis. Fatigue, depression, and anxiety are common and can deeply affect daily life, work, and relationships. Managing medications and unpredictable flare-ups of the condition adds to the emotional strain. Having a chronic inflammatory condition treated with glucocorticoids, immunosuppressants and biological medications can also increase the risk of secondary co-morbidities including cardiovascular disease, diabetes, hypertension, risk of infections and malignancies.

Experts suggest that even outside of end-of-life care, people with arthritis could benefit from support that combines Rheumatology and Palliative Care. However, current guidelines for healthcare professionals does not include arthritis when helping doctors identify who might need end-of-life care. No guidelines currently exist for Palliative Care teams on how to support people with arthritis, which can leave patients feeling their arthritis is overlooked or misunderstood.

### **Inflammatory arthritis and the potential need for palliative and supportive care.**

In preparation for this study, we conducted focus groups with people living with an inflammatory arthritis, all of whom had experience of palliative and end of life care through their life experiences (n=11). They told us they often do not mention arthritis symptoms when receiving palliative and end of life care in a hospice setting, because they assume healthcare professionals already understand the impact of their arthritis, or they are used to living with the pain and believe it is more important to tell hospice staff about the pain related to their palliative diagnosis. Palliative care professionals confirmed this, saying their focus tends to be on the most life-threatening condition. Furthermore, they described having limited knowledge about inflammatory arthritis and its impact on the individual.

In conversations with people living with inflammatory arthritis, many said they had faced moments when extra help would have made a big difference. When they learnt more about PSC, they thought this type of care would be of significant help to them. One woman described how her arthritis symptoms were so severe early on in her diagnosis that her children had to help her with basic tasks like dressing and eating. Focus group participants also spoke about future challenges they might face, especially near the end of life. They worried about pain from being unable to move, side effects from medications, and wanted to have conversations in advance about treatment options and comfort care.

Rheumatologists and palliative care teams told us they had limited knowledge about each other's specialities, which could lead to uncertainty about the optimum care for people with an inflammatory arthritis towards the end of life. For example, should arthritis medications be stopped or continued near the end of life? When should conversations about end-of-life care begin in Rheumatology practice? Despite these challenges, rheumatology and palliative care have a similar approach to care, that it is holistic, person centred and aimed at maximising quality of life. Rheumatology and Palliative Care healthcare professionals told us our work could encourage closer working between the two Specialities, as well as improve care for those with inflammatory arthritis. For example, "there's a lot of overlap of those symptoms (pain, breathlessness), and sometimes we might be treating things we know well rather

than looking a bit wider to the things we don't know so well" (Palliative Care Clinician).

General Practitioners and Community healthcare professionals told us it was important for us to also include them in our work as they care for many people towards the end of life. They would welcome guidance on inflammatory arthritis and PSC, especially on the management of medications.

### **Current evidence**

We conducted a rapid literature review at the outset of this study (parameters: English language; 2014-present; 'arthritis'; 'spondylitis'; 'ankylosing'; 'ankylosing spondylitis'; 'Palliative Care') looking for any study design that described the interaction between Rheumatology and Palliative Care, patient and/or health care professionals' perspectives on potential Palliative Care need. Only three relevant papers were identified. One was an opinion piece and two explored routine clinical data, which demonstrated symptoms in rheumatology patients that could be met by palliative care services. No qualitative research was identified, and nothing that described the patients' or healthcare professionals' perspectives in either Speciality. Of note, in 2008, the dearth of literature in this area was highlighted in the Journal of Palliative Care with the authors concluding that rheumatologists, palliative and primary care physicians should become more aware of patients with rheumatic diseases to offer them the care they need.

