### **Focus and study population**

As described, we have consulted widely with people with inflammatory arthritis, rheumatology, palliative care, primary and community healthcare professionals. They confirmed this is an important topic to investigate. They encouraged us to explore the potential value of Supportive Care, in addition to Palliative Care, as although not widely available outside of cancer services, the similarities in personal health and emotional challenges for Rheumatology patients may mean it is highly appropriate.

This study focuses on four common types of inflammatory arthritis:

- Rheumatoid Arthritis (RA)
- Psoriatic Arthritis (PsA)
- Juvenile Idiopathic Arthritis (JIA)
- Axial Spondyloarthritis (axSpa)

These conditions often involve similar symptoms, treatments, and related health issues. While there are other rare, life-threatening rheumatic diseases, this study concentrates on the more common ones to better understand how Supportive and Palliative Care could help throughout a person's life.

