#### **3.2 Objectives**

- Create 3 short videos for use within our WPs, to aid understanding and ensure consistent messaging in our project.
- Conduct semi-structured online or telephone interviews with people living with an inflammatory arthritis to understand their views of PSC, and how PSC may support them to live well throughout the course of their disease (WP1).
- Conduct an e-survey with healthcare professionals working in Rheumatology, Palliative Care, Primary Care and Community services to determine current provision of PSC for people with inflammatory arthritis and understand views about the potential value of PSC support (WP2).
- In collaboration with Public Contributors, assimilate data from WPs1 and 2 into a 'key findings' summary document and presentation, to be shared with expert stakeholders. Repeat previous rapid literature review and include any new findings in the summary document and presentation (WP3).
- Conduct four online stakeholder focus groups to agree: a) the nature and scope of 'unmet need' as described in our data; b) recommendations for future clinical practice and research, and patient identified areas of importance, which should be measured.
- Disseminate study findings.

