### 3.4 Outcomes

The primary outcomes for this research will be:

- A description of the nature and scope of unmet patient need,
- Clinical and research recommendations, informed by expert opinion and the 'six pillars' framework of the British Society of Lifestyle Medicine, which describe the potential role of PSC for people with inflammatory arthritis throughout the disease course. We will particularly consider Supportive Care, within the 'six pillars' framework, as this includes improving a person's general physical and mental health. These recommendations will be shared with people with inflammatory arthritis, clinicians, academics and service commissioners. Future work will explore how to implement the recommendations into practice to improve the lives of people with inflammatory arthritis.
- Patient identified areas of importance which should be measured in future work.

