**4.4.4. Data collection** Data from WP1 and 2 will be assimilated into a 'key findings' presentation to be shared with expert stakeholders. Pre-application rapid literature review will be repeated and any new findings included in this presentation. A summary of the project's findings, and links to the three videos used, will be sent to participants prior to the online event/s to optimise the potential for reflective and deep discussion. This summary will be used as a topic guide to steer the discussion to key questions. Focus groups will be conducted face to face (x2) and online (x2) via Microsoft Teams at a date and time convenient to participants, and following **participant consent**, recorded using embedded audio recording function. Each focus group will run for a maximum of 120 mins. Discussion will broadly focus on:

- What would 'good' look like for people with Inflammatory arthritis to live well with support from PSC services?
- How would this be measured?
- What is the current unmet need?
- What could reduce/address this unmet need in Rheumatology and Palliative care services?
- What are the challenges and barriers?
- What further clinical and/or research work is required?

After each event, the discussion will be summarised by the lead facilitator ([name] or [name]) and confirmed by members of the group. An iterative approach will be taken across these events so the final summary is representative of the discussion from all Stakeholder events. For example, in groups 2 and 3, following initial discussion and agreement of draft recommendations, the views of the previous Stakeholder group/s will be shared and added to or refined. Using transcribe function within Microsoft 365, audio data will be transcribed verbatim and analysed using inductive qualitative content analysis.

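### The rapid review to be repeated for WP3 searches on Palliative Care alone, so it is likely to under-retrieve evidence on Supportive Care, which the recommendations are meant to emphasise

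*Protocol*

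**What the plan says.** The Background (Current evidence) describes a rapid review done at the start of the study, with parameters "English language; 2014-present; 'arthritis'; 'spondylitis'; 'ankylosing'; 'ankylosing spondylitis'; 'Palliative Care". It looked for any design that "described the interaction between Rheumatology and Palliative Care, patient and/or health care professionals' perspectives on potential Palliative Care need". Its yield was: "Only three relevant papers were identified". The same paragraph adds that no qualitative work was found.

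The review is to be used again in WP3. Section 3.2 says: "Repeat previous rapid literature review and include any new findings in the summary document and presentation (WP3". Section 4.4.4 says: "Pre-application rapid literature review will be repeated and any new findings included in this presentation". Participants also receive a summary of the project's findings in advance, and of this section 4.4.4 says: "This summary will be used as a topic guide to steer the discussion to key questions".

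On scope, the study title names Palliative and Supportive Care. The Background (Focus and study population) reports of those consulted: "They encouraged us to explore the potential value of Supportive Care, in addition to Palliative Care". Section 3.4, describing the recommendations that form a primary outcome, says: "We will particularly consider Supportive Care, within the 'six pillars' framework". Section 4.5.3 repeats this emphasis for WP3 reporting. Axial spondyloarthritis is one of the four study conditions.

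**The concern.** The search and the study do not have the same scope. The study asks about two kinds of care, and the review's search term and stated target name only one. The omitted kind is the one the recommendations are to consider in particular.

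The protocol's own Background makes the omission matter. It describes supportive care as starting much earlier in the illness than palliative care. Papers on early support in arthritis are thus among those least likely to use the term *palliative care*, and among those most relevant to a study that covers the full course of disease.

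What is at stake is the briefing for the focus groups. They are asked about current unmet need and about what further clinical or research work is required. If the evidence summary is thin on supportive care because that literature was not searched for, the groups answer those questions on an incomplete basis.

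**Working it through.** There is no sample size, error rate or estimate to recompute. The check compares the stated search with the stated scope, then asks whether the protocol's own reference list can show the size of the gap.

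**1. Scope against search**

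| Element of scope | Where stated | Listed search term |
|---|---|---|
| Palliative Care | Title; 3.1 to 3.4 | Yes, the only care term |
| Supportive Care | Title; Focus and study population; 3.4; 4.5.3 | None |
| Rheumatoid, psoriatic and juvenile idiopathic arthritis | Focus and study population; 4.2.1 | *arthritis* |
| Axial spondyloarthritis | Focus and study population; 4.2.1 | *ankylosing* and *spondylitis* in part; *spondyloarthritis* not named |

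The review's stated target also names Palliative Care only, so the gap lies in what was sought as well as in the term used.

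**2. What follows for retrieval.** Operators, fields and databases are not given. Assume, as is usual, that a record needs a disease term and the care term.
- An arthritis paper on supportive care that also mentions palliative care can be found.
- One that does not mention palliative care is missed.
- If *Palliative Care* was run as an exact phrase, wording such as *palliative and supportive care* does not match it either.

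**3. What follows for the period covered.** Only new findings are to be added. Supportive-care papers from 2014 up to the first search were outside that search. They would stay outside a repeat with the same terms.

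**4. Can the reference list size the gap?** The listed terms were matched against titles.
- References 29, 31 and 32 are the three papers the review kept. None has a listed disease term in its title, and reference 31 also lacks the phrase *palliative care*. Retrieval evidently did not rest on titles alone, so a title check cannot show what the search misses.
- References 10, 14 and 41 have *supportive care* but not *palliative care* in the title. They concern oncology, incurable cancer and a generic definition, and none has a disease term. A search widened to supportive care would not match them by title either.
- References 18 and 19 have *spondyloarthritis* in the title. *Arthritis* matches it as a substring but not as a whole word. Neither title has a care term, so the widened search would not match them by title either.
- Reference 25, a survey of psychological support in inflammatory arthritis, matches *arthritis* but neither care phrase.

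No listed paper can therefore be shown to be a relevant one that was lost. The mismatch of scope is established; the number of papers missed is not.

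**The case against.** The strongest case against has four parts.

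- **The review did what it set out to do.** It was a rapid review whose stated target was Palliative Care, and its care term matches that target. This is fair for the first run. It does not justify reusing the same target to brief groups whose recommendations are to stress Supportive Care.
- **The parameters are a one-line list, not a full strategy.** To repeat a review does not forbid adjusting its terms. That is true, but no adjustment is stated. This point stands fully for spondyloarthritis: whether *arthritis* captures it depends on unstated settings, and *ankylosing* and *spondylitis* cover part of the ground. That limb is secondary.
- **No missed paper has been shown.** This stands, and it limits the claim to likely under-retrieval.
- **The consequence is diluted.** The WP3 presentation is built from WP1 and WP2 data, which collect views on supportive care directly. The discussion areas are already listed in section 4.4.4, and the participants bring their own expertise. This stands and keeps the point modest.

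A reader might infer more: that the search cannot find supportive-care evidence, that it is blind to half the topic, or that stakeholders will be told little exists. The documents support none of these. Papers mentioning both kinds of care are retrievable, no share of the topic is stated, and sections 3.2 and 4.4.4 promise only that new findings will be included. Nor do the documents date the search relative to the advice to include Supportive Care, so it cannot be said that the scope was widened afterwards.

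**Conclusion.** The point holds as a mismatch between a stated method and the study's own scope. As specified, the repeated review is likely to under-retrieve evidence on supportive care in inflammatory arthritis, and the three-paper yield supports scarcity for Palliative Care only. This rests on two assumptions: that the repeat uses the listed terms, since no change is stated, and that a care term was required for retrieval.

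The size in papers is unknown and cannot be derived from the documents. The effect is confined to one input to the WP3 briefing. It touches no estimate, sample size or participant procedure. It is worth correcting before WP3 because the change is small, but it does not threaten the study as a whole.

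**What to change.** - In sections 3.2 and 4.4.4, replace the plain repeat with an updated search that adds *supportive care*. As a secondary point, add *spondyloarthritis*, so that its capture no longer depends on search settings.
- Widen the review's stated target to include Supportive Care. Otherwise papers found by the new term would be screened out.
- Apply the added terms to the whole period from 2014, not only to the time since the first search.
- Until this is done, limit the scarcity statement in the Background (Current evidence) to Palliative Care.

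The cost is some extra screening, presumably by the Research Fellow; the documents give no figure for the time needed. The three-paper statement may have to be revised. Section 4.4 places WP3 in months 13 to 17, so the wording can be changed before the search is run.
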